SABR is thought to cause ablation of all tissue within the target RT field. However immediate post-SABR tumor biopsy specimen has never been evaluated; it is therefore uncertain if immunohistochemistry (IHC) staining will reveal any identifiable remnant cell population in the immediate period after SABR. In this study, TCR sequencing of FFPE tissue is first priority. This is followed by WES of FFPE tissue in priority.

Additional FFPE core tissue will be used to evaluate the presence of leukocytes on Hematoxylin & Eosinophil (H&E) staining. If leukocytes are present, immunohistochemical staining and analysis may include but is not limited to CD4+ T-cells, CD8+ T-cells, PD-L1, and FoxP3 transcription factor.

The presence of specific key tumor infiltration lymphocytes (TILs) will first be assessed with immunohistochemical (IHC) staining of CD4 T-cells and cytotoxic CD8 T-cells. The respective T-cell density will be determined by our pathologists. We will then evaluate the presence of FoxP3, a transcription factor in CD4 T-cells, and PD-L1, a key checkpoint-related cell surface marker, in the tumor. If viable tumor cells are present, pathologists will assign an intra-tumoral and peri-tumoral immune cell infiltrate grade of (0) none, (1) rare (2) focal or (3) severe diffuse infiltration of lymphocytes. Our lung cancer pathologists will designate 3 representative fields to be evaluated by image analysis, which will allow for the data to be reported as a percentage of area (intra- and peri-tumoral) with positive T-cell infiltrate staining. Peri-tumoral versus intra-tumoral infiltrates will be scored, since these staining patterns have been shown to correlate with clinical outcomes. Pathologic response will also be scored as percentage of viable tumor, averaged from 3 areas of the FFPE-core biopsy sample. Drs. [name] and [name] have experience in performing reviewing IHC staining of tissue.

[figure not shown]

Figure 2: Immunofluorescence Pre and Post PD-1 in NSCLC patient with treatment response.

Increase in CD8+ T-cells post treatment

3.3.5: Correlate dual-energy CT imaging characteristics with radiation dose, and early post-SABR pathologic outcomes.

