If the study ends or if a participant's participation in the study ends prematurely, patients enrolled on the trial currently receiving treatment will complete their standard of care protocol treatment, but will not receive additional study biopsy, blood work, or imaging tests. They will return for routine care and follow-up with their treating physician.

Replacement of Subjects

If a subject withdraws from the study, that subject will be replaced. In the circumstance where a study subject does not have the post-SABR biopsy obtained, that subject will be replaced. For patients who do not have the post-SABR biopsy obtained, their data will not be used in the analysis.

Protocol Enrollment Completion

Up to 40 patients will be screened. This study will complete subject enrollment and accrual when there are a total of 10 patients accrued with BOTH pre- and post-SABR biopsies obtained.

5 Inclusion/Exclusion Criteria

Inclusion Criteria

1. Written informed consent obtained from the subject prior to performing any protocol-related procedures, including screening evaluations
2. Age > 18 year
3. Histologically or cytologically confirmed non-small cell lung cancer after initial biopsies
4. Patient with accessible tumor for biopsy by transthoracic or endobronchial approach as determined by an interventional radiologist and or interventional pulmonologist.
5. Patient is to have sufficient initial core biopsy samples for tissue analyses
6. AJCC 8th edition stage I lung cancer (clinical T1a-T2a N0 M0, ≤4cm)
7. Adequate normal organ and marrow function as defined below:

Hemoglobin	≥ 9.0 g/dL
Absolute neutrophil count (ANC)	$\geq 1.5 \times 10^9/L$ (> 1500 per mm 3)
Platelet count	$\geq 50 \times 10^9/L$ ($>50,000$ per mm 3)
Creatinine	≤ 2 mg/dL

for the dual-enhanced CT portion of the study;
Creatinine is not required for inclusion into the trial
8. Patient with tumor amenable to SABR treatment as determined by a radiation oncologist
9. Subject is willing and able to comply with the protocol for the duration of the study including undergoing treatment and scheduled visits and examinations including follow up.
10. Post-menopausal status or negative urinary or serum pregnancy test for female pre-menopausal subjects. Women will be considered post-menopausal if they have been amenorrheic for 12 months without an alternative medical cause.

Exclusion Criteria

1. Primary tumors not amenable to serial core biopsies.

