2. Prior thoracic radiation in the region that will be treated by SABR.
3. Patient may not be receiving any other concurrent investigational agents or chemotherapy.
4. Patient may not be receiving or received immunotherapy.
5. Patients may not be on or use steroids within 14 days before radiation, and from the duration of radiation to the time of the post-SABR biopsies and blood samples. The following are

exceptions to this criterion: Intranasal, inhaled, topical steroids, or local steroid injections (e.g., intra articular injection).

6. Female patients who are pregnant from screening to completion of SABR

See Appendix for AJCC 8 NSCLC cancer staging and Screening Procedure Outline.

6 Drugs/ Substances/ Devices

- a. The rationale for choosing the drug and dose or for choosing the device to be used. -N/A
- b. Justification and safety information if FDA approved drugs will be administered for non-FDA approved indications or if doses or routes of administration or participant populations are changed. -N/A
- c. Justification and safety information if non-FDA approved drugs without an IND will be administered. -N/A

7 Study Statistics

a. Primary outcome variable.

Primary Objective: Examine the T-cell receptor profile changes induced in the tumor after SABR. If TCR next generation sequencing analysis of post-SABR tumor is feasible, a significant TCR profile change is defined as a multi-fold increase in the frequency of identified TCR complementarity determining region 3 (CDR3) regions present in post-SABR tumor biopsies when compared to control pre-SABR tumor biopsies.

b. Secondary outcome variables.

Secondary Objectives:

1. Evaluate candidate tumor antigens (mutation associated neo-antigens, MANAs, and tumor associated neo-antigens, TAAs) released from the tumor by SABR.
2. Describe the influx of key tumor infiltrating lymphocytes in the tumor after SABR.
3. Link tumor antigen recognition by activated post-SABR peripheral T-cells with candidate pre-treatment MANAs and TAAs primed by SABR.
4. Evaluate the relationship between dual-energy (DE) CT imaging characteristics, radiation dose, and early post-SABR pathologic outcomes after treatment with SABR.
5. Evaluate the safety of post-SABR biopsies

c. Statistical plan including sample size justification and interim data analysis.

Primary Objective:

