The primary objective is to estimate the change of T cell receptor level between pre-SABR and post-SABR. A greater increase in T cell receptor level suggests a greater biological effect. With 10 analyzable patients, the change between pre-SABR and post-SABR could have an estimation precision (half of the 2-sided 90% confidence interval) of 0.58 standard deviation (with appropriate transformation when the distribution of T cell receptor level does not follow a normal distribution).

Sample Size Justification: Approximately 35 patients with medically inoperable stage I NSCLC are treated at Johns Hopkins with SABR per year and 75 patients with medically operable stage I NSCLC treated a year. We have planned an accrual rate of 1-2 patients per month and expect enrollment to be complete within 1 years.

Secondary Objectives:

For all secondary endpoints, descriptive analysis but no formal hypothesis testing will be performed given the nature of exploratory analysis. These summaries will be computed for each evaluable patient at time-points before and after SABR. Plots will be used to show the changes in immune response over time both for each individual. For each patient, comparisons in the pre and post-SABR responses will be compared using paired t-tests (or Wilcoxon signed rank tests if appropriate) for continuous variables and McNemar's test for dichotomous or categorical variables. Associations between immune responses will be explored graphically (e.g. scatterplots, boxplots) and numerically (e.g. correlations, χ^2 tests).

Additional pictorial displays will be explored to evaluate the characteristics of iodine uptake after delivery of SABR in relation to SABR dose gradients.

- d. Early stopping rules.

For the primary objective: To minimize unnecessary intervention, we will monitor the post-SABR core biopsy failure rate by a Bayesian stopping rule. We will accrue patients to a different post-SABR biopsy time point, if the posterior probability of unsuccessful biopsies being larger than 70% is 70% or higher. We assume *a priori* that the post-SABR biopsy has an average of 50% successful biopsies, and there is about 22% chance that the unsuccessful biopsy rate is 70%. Based on such rules, we will assess the feasibility when 5 and 10 patients get biopsy, and determine post-SABR core biopsy is infeasible as inability to estimate T cell receptor level and change the timing of biopsies if none of 5, or less than 2 of 10 successful biopsies are observed.

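### By the rule in section 7c the ordered 0–3 infiltrate grade falls to McNemar's test, which suits it poorly; the signed-rank test named in the same sentence would suit it better

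*Combined protocol and SAP*

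**What the plan says.** The rule is in section 7c, under Secondary Objectives. Pre- and post-SABR responses are compared with "paired t-tests (or Wilcoxon signed rank tests if appropriate) for continuous variables and McNemar's test for dichotomous or categorical variables". The Wilcoxon test is offered as the alternative to the t-test within the continuous group. Ordered variables are not mentioned, and no multi-category extension of McNemar's test is named. The same paragraph declares all secondary analyses descriptive, without formal testing, and plans plots for individual patients.

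The measure is in section 3.3.4, which concerns pre/post change in the tumor. Pathologists assign, for intra-tumoral and peri-tumoral tissue, an "immune cell infiltrate grade of (0) none, (1) rare (2) focal or (3) severe diffuse infiltration of lymphocytes". No cut-point for this grade appears anywhere. It serves secondary objective 2 (sections 2 and 7b): "Describe the influx of key tumor infiltrating lymphocytes in the tumor after SABR".

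The same section also provides T-cell density and image-analysis data "reported as a percentage of area (intra- and peri-tumoral) with positive T-cell infiltrate staining".

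Grading is conditional: "If viable tumor cells are present, pathologists will assign an intra-tumoral and peri-tumoral immune cell infiltrate grade". Of tissue taken soon after SABR, the section says that "it is therefore uncertain if immunohistochemistry (IHC) staining will reveal any identifiable remnant cell population in the immediate period after SABR". Tissue is also rationed: "In this study, TCR sequencing of FFPE tissue is first priority. This is followed by WES of FFPE tissue in priority".

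**The concern.** The grade has four ordered levels, so paired data form a 4x4 table. McNemar's test in its usual form takes a 2x2 table, which requires splitting the grade at one of three places (≥1, ≥2 or ≥3). A one-grade change crosses exactly one of these, so any single cut ignores every one-grade change made elsewhere on the scale. With no cut stated, it could be chosen after the data are seen.

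If categorical is instead taken to mean the multi-category form, Bowker's test of symmetry, no cut is needed. That test does not use the order of the grades, however, so rises and falls at different levels add to the statistic when they should offset. Its chi-square reference is also doubtful with so few pairs.

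What is at stake is the size, and in some data the apparent direction, of a descriptive p-value for one of several measures under secondary objective 2.

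**Working it through.** **The plan's own figure.** The only precision figure in section 7c belongs to the primary objective: a 90% confidence half-width of 0.58 SD with 10 patients. It reproduces: t(0.95, 9 df)/√10 = 1.833/3.162 = 0.580. This point does not affect it. The plan gives no figure for the grade.

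**Inputs.** The number of pairs is at most 10, because enrollment ends when "there are a total of 10 patients accrued with BOTH pre- and post-SABR biopsies obtained" (section 4, Protocol Enrollment Completion). Grades run from 0 to 3 (section 3.3.4). The documents give no baseline grades, so every data set below is constructed.

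**Formulas.**
- Exact McNemar: two-sided binomial(0.5) on the patients who cross the cut. With d crossings all one way, p = min(1, 2 × 0.5^d).
- Bowker: sum over pairs of grades of (up − down)²/(up + down), referred to chi-square. The degrees of freedom (df) are either the number of non-empty pairs or all 6.
- Exact signed-rank: all sign patterns enumerated with midranks, unchanged pairs dropped. When every change is one grade, this equals the sign test.

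**Main example (A).** Ten pairs, baseline grades 0/1/2/3 in 2/4/3/1 patients. The nine patients below grade 3 each rise one grade.
- McNemar at ≥1, ≥2, ≥3 has 2, 4 and 3 crossings: p = 0.50, 0.125, 0.25.
- Bowker: 2²/2 + 4²/4 + 3²/3 = 9. p = 0.029 on 3 df, 0.17 on 6 df.
- Signed-rank: 2/2⁹ = 0.0039.

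Bowker's expected cell counts under symmetry are only 1, 2 and 1.5 here. Exact enumeration gives 2³/2⁹ = 8/512 = 0.016, matching neither chi-square value. Of those 8 arrangements only 2 have all nine patients moving the same way, which shows that the test ignores order.

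**Other constructed cases.**

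| Case | McNemar ≥1 | ≥2 | ≥3 | Bowker, non-empty df / 6 df | Signed-rank |
|---|---|---|---|---|---|
| A | 0.50 | 0.125 | 0.25 | 0.029 / 0.17 | 0.004 |
| B: baseline as A; seven rise, one falls, two stay | 1.0 | 0.25 | 0.50 | 0.15 / 0.50 | 0.070 |
| C: all 10 start at grade 1; six rise, two fall, two stay | 0.50 (down) | 0.031 (up) | 1.0 | 0.018 / 0.24 | 0.29 |
| D: 7 pairs, baseline 1/3/2/1; six rise | 1.0 | 0.25 | 0.50 | 0.11 / 0.42 | 0.031 |

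- B: crossings up/down are 2/1, 3/0 and 2/0. Bowker = 1/3 + 3 + 2 = 5.33. Signed-rank = 2(1 + 8)/256 = 18/256.
- C: Bowker = 6²/6 + 2²/2 = 8. On 2 df, p = e⁻⁴ = 0.018; on 6 df, e⁻⁴(1 + 4 + 8) = 0.24. Signed-rank = 2(1 + 8 + 28)/256 = 74/256.
- D: crossings are 1, 3 and 2. Bowker = 1 + 3 + 2 = 6. Signed-rank = 2/2⁶.

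In C the cut decides both the strength and the direction of the result. Bowker on 2 df is small because the rises and falls add, although the net movement is modest. A poor choice of test can therefore overstate as well as understate the evidence.

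With 5 gradeable pairs, neither exact McNemar nor signed-rank can go below 2/2⁵ = 0.0625, so the choice matters little.

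**The case against.** The strongest reply is that nothing depends on this. Secondary analyses are descriptive, there is no alpha, power or decision rule for the grade, and individual plots are planned. The grade is not listed as an outcome in section 7b; it appears only in section 3.3.4. Density and percent stained area measure the same infiltrate and are continuous, so they have a suitable test. No text commits specifically to a p-value for the grade. All of this stands and sets the weight of the point. It does not give the grade a fitting analysis, and the same paragraph that calls the work descriptive goes on to name tests.

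A reader might infer that the plan has no route at all for ordered scores, or that it requires a 2x2 test at a hidden cut. The documents support neither. The rule names categorical alongside dichotomous variables, which may mean the multi-category form, and that form needs no cut. An analyst might also read the qualifier on the Wilcoxon test as covering the grade. The sentence is loosely worded in any case: it speaks of paired tests for each patient, which cannot be meant literally. What survives is that the rule as written leads to a test that either needs an unstated cut or ignores order.

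The examples are also constructed and mostly show uniform one-grade rises. That is fair; they show what can happen and say nothing about how likely it is.

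**Conclusion.** The point holds as a small improvement of the lowest severity. Following the stated rule gives a poorer analysis of the 0–3 grade than the signed-rank test that the same sentence already names. In the main example the spread is 0.125 to 0.50 for McNemar by cut and 0.029 to 0.17 for Bowker by degrees of freedom, against 0.004 for signed-rank. These values rest on assumed baseline grades and changes. The conditions on grading and the tissue priority may leave fewer than 10 gradeable pairs, and the benefit shrinks as pairs are lost.

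A reader might go further and infer that secondary objective 2 is compromised. That is not supported, because its continuous measures are unaffected and no decision rests on the grade.

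**What to change.** Add one sentence to section 7c, for example: *Ordered scores, including the intra-tumoral and peri-tumoral 0–3 infiltrate grades taken separately, are compared before and after SABR with the exact Wilcoxon signed-rank test (midranks, unchanged pairs dropped); the numbers of patients who rise, fall or stay the same and the number of gradeable pairs are reported, and p-values are descriptive.* Keep McNemar's test, in exact form, for binary items. If a dichotomised grade is also wanted, state its cut before the data are seen.

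The cost is one sentence, with no new patients, tissue or data. The drawback is that the signed-rank test counts a two-grade change as larger than a one-grade change. The rise, fall and stay counts let readers check the result without that assumption.

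### Section 7c offers chi-square tests as an example for exploring associations in 10 patients; for some sparse tables the uncorrected p-value is far too small, and naming exact tests takes one sentence

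*Combined protocol and SAP*

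**What the plan says.** Section 7c, Secondary Objectives, opens with the status of these analyses: "For all secondary endpoints, descriptive analysis but no formal hypothesis testing will be performed given the nature of exploratory analysis". The same paragraph then names methods. Continuous pre/post comparisons get paired t-tests, with a signed-rank alternative. Paired categorical data get "McNemar's test for dichotomous or categorical variables". For links between readouts: "Associations between immune responses will be explored graphically (e.g. scatterplots, boxplots) and numerically (e.g. correlations, χ^2 tests").

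The number of patients is fixed elsewhere. Section 4, Protocol Enrollment Completion, closes accrual "when there are a total of 10 patients accrued with BOTH pre- and post-SABR biopsies obtained". Under Replacement of Subjects: "For patients who do not have the post-SABR biopsy obtained, their data will not be used in the analysis". The precision statement in 7c also uses 10 analysable patients.

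For categorical data the section mentions no exact test, continuity correction or check on expected counts. It does not say which version of McNemar's test is meant.

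**The concern.** The chi-square p-value is a large-sample approximation, and 10 patients split over four or more cells is a very small sample for it. Some secondary readouts invite such tables. Section 3.3.4, for example, has pathologists grade the lymphocyte infiltrate on four levels (0 to 3), which gives tables sparser than 2x2.

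At stake is how a coincidence in one or two patients would look on paper. Secondary objective 3 seeks to link T-cell reactivity with candidate antigens, and the abstract says that the results may inform later trials with checkpoint antibodies. An exploratory p-value of 0.0016 is easily carried forward, even when it rests on a single patient who has two uncommon features.

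**Working it through.** **Inputs.** N = 10 (section 4, Protocol Enrollment Completion; section 7c). Chi-square as an example method, and McNemar's test with no version stated (section 7c). Two assumptions are not in the documents: the conventional rule that every expected count be at least 5, and a nominal 5% level. The plan sets no significance level for these analyses.

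**The plan's own figure.** Section 7c gives a 90% half-width of 0.58 SD. With t(0.95; 9 df) = 1.833, 1.833/√10 = 0.580. It reproduces and confirms N = 10. The documents give no figure for the chi-square or McNemar tests.

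**Expected counts.** The four expected counts sum to 10, so the smallest is at most 10/4 = 2.5, reached at margins 5/5 by 5/5. All four can be 5 or more only if N ≥ 4 × 5 = 20. Fewer evaluable patients would lower the counts further.

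**Single tables.** For a table (a,b;c,d), uncorrected chi-square = N(ad − bc)²/(product of the four margins).

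| Table | Chi-square | Uncorrected p | Yates p | Fisher p |
|---|---|---|---|---|
| (1,0;0,9) | 10 × 81/(1×9×1×9) = 10.00 | 0.0016 | 0.160 | 0.100 |
| (1,0;1,8) | 10 × 64/(1×9×2×8) = 4.44 | 0.035 | 0.429 | 0.200 |
| (3,0;2,5) | 10 × 225/(3×7×5×5) = 4.29 | 0.038 | 0.168 | 0.167 |
| (5,0;0,5) | 10 × 625/(5×5×5×5) = 10.00 | 0.0016 | 0.011 | 0.0079 |

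The exact values can be checked by hand. In the first row the chance that the two single features fall on the same patient is 1/10. In the third row it is 2 × C(5,3)/C(10,3) = 20/120 = 0.167.

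**Error given the margins.** Up to symmetry there are 15 margin patterns for N = 10. The table shows the probability, under no association, that the uncorrected test gives p < 0.05.

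| Smaller row and column margins | Error |
|---|---|
| 1 and 2 | 0.200 |
| 3 and 5 | 0.167 |
| 1 and 1 | 0.100 |
| 4 and 4 | 0.076 |
| 2 and 3 | 0.067 |
| five patterns: 2 and 2, 3 and 3, 3 and 4, 4 and 5, 5 and 5 | 0.008 to 0.048 |
| five patterns: 1 and 3, 1 and 4, 1 and 5, 2 and 4, 2 and 5 | 0 |

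For the top row, the only table that rejects is (1,0;1,8), with probability 2/10 = 0.20. The maximum over all patterns is 0.048 for Fisher and 0.022 with the Yates correction.

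**All tables.** There are 246 2x2 tables with N = 10 and non-zero margins. Uncorrected chi-square gives p < 0.05 in 62 and Fisher in 30; the other 62 − 30 = 32 have a Fisher p of at least 0.05. No table has a Yates p below 0.05 with a Fisher p of 0.05 or more.

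**Averaged over tables.** With the two features independent and each marginal rate between 0.02 and 0.50, the false-positive rate of the uncorrected test is at most 0.058, reached with both rates at 0.16.

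**McNemar.** The uncorrected statistic is (b − c)²/(b + c), where b and c are the two discordant counts.
- 4 against 0: 16/4 = 4.0, p = 0.046; exact 2 × (1/2)⁴ = 0.125.
- 5 against 0: 25/5 = 5.0, p = 0.025; exact 2 × (1/2)⁵ = 0.0625.
- 7 against 1: 36/8 = 4.5, p = 0.034; exact 2 × 9/256 = 0.070.

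Given the number of discordant pairs, the uncorrected error exceeds 5% only at 4, 5 and 8 pairs (0.125, 0.0625 and 0.070). Averaged over the number of pairs it is at most about 0.053. The corrected and exact versions never exceed 0.039.

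**The case against.** The strongest reply is that the plan disclaims formal testing for these endpoints before it names any test. Chi-square follows an e.g., alongside plots and correlations, with no significance level or decision rule. Many of the readouts are continuous (clone frequency, T-cell density, percentage of stained area, percentage of viable tumour, iodine uptake), and no specific 2x2 association is planned. This stands and sets the priority. It does not remove the point, because the named tests still produce p-values, and calling a p-value exploratory does not make 0.0016 a fair summary of one coincident patient.

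A second reply is that the average error is close to nominal. That is correct. But a reader sees one observed table, and at some margins the error given those margins is several times 5%.

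Three stronger readings are tempting, and the documents do not support them:
- A reader might infer that the plan prescribes a large-sample McNemar test. It names only McNemar's test, which has an exact form. The version is unspecified, not wrong.
- A reader might infer that chi-square is invalid for every table here. No table meets the rule of 5, but that is a convention. A looser rule (every expected count at least 1) admits some tables, and in 10 of 15 margin patterns the error stays below 5%.
- A reader might infer that significant links will be claimed on this basis. The plan does not say so, and it does not say that the uncorrected version will be used.

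**Conclusion.** The point holds as a low-priority improvement. Chi-square is a poor example to name for 10 patients. Uncorrected, it can understate the p-value roughly sixtyfold in the sparsest table (0.0016 against 0.10), and its error given the margins reaches 20%. The excess is confined to 5 of 15 margin patterns, averages out to at most about 5.8%, and disappears with a continuity correction.

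The size of the problem assumes that the uncorrected version is run, that p-values are printed, and that readers set them against 5%. The primary estimate, its 0.58 SD precision and both stopping rules use neither chi-square nor McNemar's test, so none of them is affected.

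**What to change.** In section 7c, replace the chi-square example with Fisher's exact test for 2x2 tables and the Fisher-Freeman-Halton test for larger ones, such as those using the four-level infiltrate grade. Alternatively, report the counts without p-values. In the same sentence, state that McNemar's test for dichotomous pre/post variables will be run in its exact binomial form. Keep all of it labelled exploratory.

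The cost is one sentence, with no extra data, patients or procedures. Some nominal p-values become less favourable, and exact tests are conservative at this size: at several margins no table of 10 can reach p < 0.05. That is a further reason to show the counts whichever option is chosen.
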